EVALUATION PROTOCOL

Building Positive Relationships with your Teen: Evaluating the Teen Triple P Programme

CEDAR, University of Warwick

Principal investigators: [name] and
[name]

Building Positive Relationships with your Teen: Evaluating the Teen Triple P Programme

Evaluation protocol

Evaluating institution: CEDAR, University of Warwick

Chief investigator(s): [name] and [name]

Sponsor	University of Warwick
Sponsor ref	SOC.08/22-23
REC ref	23/LO/0435
IRAS number	324435
ISCTRN ref	tbc

Project title¹	Building Positive Relationships with your Teen: Evaluating the Teen Triple P Programme
Developer (Institution)	Triple P UK
Evaluator (Institution)	CEDAR, University of Warwick
Principal investigator(s)	[name] and [name]
Protocol author(s)	[name], [name], [name], [name], [name], and [name]

¹ Please make sure the title matches that in the header and that it is identified as a randomised trial as per the CONSORT requirements (CONSORT 1a).

Trial design
	
Two-armed cluster randomised controlled trial with random allocation at the family level (families as clusters)

Trial type
	
Efficacy with internal pilot

Evaluation setting
	
Family / local authority

Target group
	
Families (parents/carers) of 11 to 15 year olds at the edge of care

Number of participants
	
275 families, up to 412 parents/carers

Primary outcome and data source
	
6 months post-randomisation SDQ externalising score – Parent report

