Determine whether there is a benefit of support as usual (SAU) plus Standard Teen Triple P (TEEN TRIPLE P) over support as usual (SAU) in improving parent/carer rated adolescent externalising behaviour problems at 6-months post-randomisation in adolescents at the edge of care.

Secondary objectives (SO):

1. Complete an Internal Pilot in the first year to inform the decision as to whether proceeding with a definitive trial is warranted and feasible.
2. Determine whether TEEN TRIPLE P + SAU, (a) reduces parent reported adolescent internalising behaviour and increases prosocial behaviours at 6 months and 12 months post-randomisation, and parent reported adolescent externalising behaviour at 12 months post-randomisation, and (b) reduces adolescent reported externalising and internalising behaviour problems and increases prosocial behaviours at 6 and 12 months post-randomisation, (c) improves parenting practices, parent self-regulation, interparental relationships, parental-adolescent relationships and parental well-being at 6 and 12 months post-randomisation, decreases adolescent reported antisocial behaviours at 12 months post-randomisation, and (d) reduces the chance of a child going into out of home placement over a 12 month period.
3. Carry out exploratory sub-group analyses of outcomes by adolescent learning disability status and whether living with foster versus biological/adoptive parents.
4. Monitor and report and adverse events related to TEEN TRIPLE P.
5. Complete a process evaluation using key indicators drawn from the logic model, including an evaluation of acceptability and the experiences of parents/carers, adolescents with a broad range of ethnic and diverse backgrounds, and other key stakeholders (e.g., practitioners, delivery team), and fidelity of delivery of TEEN TRIPLE P.

Internal pilot

The design incorporates an internal pilot in the first year with progression criteria (Avery et al., 2017) to examine whether moving on to complete a definitive trial is warranted. The proposed criteria are:

Recruitment

(i) 50% of overall final trial target (families) within first 6 months of recruitment to the trial (green=80 to 100% (n=99)); amber=60 to 79%; red=<60%);

Randomisation

(i) Proportion of recruited families randomised (green= $\geq 90\%$; amber=50-89%; red=<49%).

Fidelity and adherence (first 3-4 months of those randomised to TEEN TRIPLE P who will have completed intervention by the progression decision point)

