(i) Fidelity assessed according to a fidelity checklist (developed in collaboration with the delivery team, prior to the internal pilot – see later in Process Evaluation) (green= ≥ 80 of sessions meet criteria; amber=50-79%; red=<50%);

(ii) Adherence: session attendance (green= $\geq 75\%$ of families attend at least the first 8 of the 10 sessions; amber= 50-74%; red=<50%).

Outcomes

(i) Data completeness for the Strengths and Difficulties Questionnaire (SDQ) parent reported young person externalising problems score at baseline: green= $\geq 75\%$; amber=50-74%; red=<50%.

The final progression criterion will be an assessment to confirm that the support in the intervention arm is sufficiently different to the control arm. This will be an assessment based primarily on a SAU survey.

Information from the SAU survey will be examined for any overlap with the content of the TEEN TRIPLE P intervention.

Design

A two-arm cluster (with families as the clusters) randomised efficacy RCT of Standard Teen Triple P (TEEN TRIPLE P) plus SAU vs. SAU alone, running over 40 months, involving parents and foster carers of young people aged 11-15 years on the edge-of-care. There will be a 6- and 12-month follow-ups, and a process evaluation and internal pilot.

Procedure

Parents and foster carers identified by case-holding social workers and edge-of-care teams across six local authorities (Cambridgeshire, Peterborough, Birmingham, London Borough Merton, Gloucestershire, and Wirral). Participants (primary parents/carers) will be screened by case-holding social workers and edge of care teams to check initial eligibility. Those who are likely to be eligible will be invited to take part in the trial.

All participants who agree to participate and for whom consent has been given will be screened to ensure they meet the eligibility criteria. Consent from those with parental responsibility is required, and young person assent when under 16 years of age – for research participation by young people. If the local authority has parental responsibility, then the social worker would consent to the inclusion of the young person on behalf of the local authority.

Baseline assessments will be completed prior to randomisation. Families randomised to the intervention arm will receive TEEN TRIPLE P as well as existing edge-of-care services (SAU), and those randomised to the control arm will receive SAU alone.

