The appointment with the research assistant can be made in two ways, the research assistant can contact the participant/parent or guardian to arrange the appointment (using contact details from the screening log), or the participants/parent or guardian can get in touch directly with the research assistant to request the appointment. Alternatively, consent can be obtained directly using an online form, prior to baseline data collection if the participant preferred.

The local Authority will be advised of the outcome of the eligibility assessment.

Contact logs

A contact log of all ineligible and eligible but not consented/not approached will be held in a secure online database that can be accessed by the trial team and the research department so that any biases from differential recruitment will be detected. The log will be completed by Local Authority staff. When at site, identifiable information should only be entered on these for those CYP who say that they want to take part, for those who do not want to take part only no-identifiable information (e.g. ID) will be held on the screening log. Contact log data will be monitored and a TMG/TSC report will be produced for each meeting containing summaries of screened, recruited, refusal of participants. Plots of the actual vs predicted recruitment will also feature in each report.

Recruitment rates

A total of 412 participants (parent/guardians) will be recruited at an expected rate of 34-35 per month, across six authorities (approximately 6 per Local Authority site, per month), over 12 months. 206 participants will be recruited in the pilot phase, and 206 in the main trial phase.

Informed consent

The parent/guardian and CYP participants will have been sent a Participant Information Sheet and copy of the consent/assent form prior to the first appointment taking place and given sufficient time to read the information. There will be two versions of the Participant

Information Sheet for CYP who take part in the main trial, one for 11 to 15-year-olds, and one for 16-year-olds if they turn 16 during the trial. Trial information will be appropriately adapted for use by younger CYP. We will provide trial information in alternative formats (e.g., audio file, video) and make these available to all participants.

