The trial protocol states that, “Determine whether there is a benefit of support as usual (SAU) plus Standard Teen Triple P (TEEN TRIPLE P) over support as usual (SAU) in improving parent/carer rated adolescent externalising behaviour problems at 6-months post-randomisation in adolescents at the edge of care”. Therefore, the trial is on the basis of superiority of the support with additional therapy arm of the trial.

Pilot analysis

Sample size will not be recalculated at any point in the trial, regardless of speed of recruitment. Tables of summary statistics will be produced on all outcomes (primary and secondary).

Characteristics of each trial arm group will be summarised descriptively, both as randomised and as analysed in the primary analysis. Categorical data will be summarised by numbers and percentages. Continuous data that follow a normal distribution will be summarised using means and standard deviations while skewed continuous variables will be summarised using medians and inter-quartile ranges. Histograms and boxplots will be used to check the distribution and possible outliers for continuous variables.

Regarding the sample size for internal pilot, we have pragmatically specified 50% of the overall sample as the recruitment window overall is quite short. We anticipate that recruitment will gather pace so have opted for a longer pilot phase and consequently, a bigger proportion of the final sample. This number does allow us to provide more useful/reliable information from the pilot to assess progression criteria including randomisation and attrition rates. This also follows recommendations from Eldridge et al (2016) that larger pilots for

cluster RCTs are typically more informative and do not follow the same rules of thumb from pilot studies of individually randomised trials.

Internal pilot studies may serve a number of functions and in this case the main functions relate to feasibility of aspects such as recruitment that will not change trial design. Assumptions around sample size can be checked as a part of an internal pilot (Wittes & Brittain, 1990) but we have not proposed to do that given that resources are fixed at the outset of the trial as defined by the funder, YEF.

Timing of final analysis

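### The internal pilot's green recruitment count (n=99) is 72% of its own target, not the 80% printed beside it; secondarily, no pilot criterion covers attrition

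*Protocol*

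**What the plan says.** **Recruitment.** The Protocol (Internal pilot, Recruitment) defines the criterion as "50% of overall final trial target (families) within first 6 months of recruitment to the trial (green=80 to 100% (n=99", followed by "amber=60 to 79%; red=<60"%. The Protocol summary table gives the overall target as "275 families, up to 412 parents/carers", and Table 2 also has 275 clusters. The pilot is half the trial elsewhere too. The Protocol's Recruitment rates section states that "206 participants will be recruited in the pilot phase, and 206 in the main trial phase", and the SAP's Pilot analysis section says "we have pragmatically specified 50% of the overall sample as the recruitment window overall is quite short".

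**Outcome data.** The only outcome-data criterion (Internal pilot, Outcomes) is completeness of the SDQ "parent reported young person externalising problems score at baseline", with green at 75% or more, amber 50 to 74% and red below 50%. The Procedure section adds: "Baseline assessments will be completed prior to randomisation". The SAP justifies the pilot's size partly because it helps to "assess progression criteria including randomisation and attrition rates". The other listed criteria cover randomisation, fidelity, session attendance and the contrast with support as usual. None concerns follow-up.

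**The concern.** A traffic-light criterion works only if its count and its percentage describe the same boundary. Here they do not, so a result in the disputed range could be reported as green or as amber, each time with support from the text.

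The second issue is what the criteria leave out. The primary endpoint is at 6 months, the sample size allows for 20% of families being lost, and the Protocol's Risks section lists attrition among the main risks. The SAP implies that attrition is a progression matter, yet the Protocol sets no threshold for it. A measure taken before randomisation cannot show whether families stay in the trial. The pilot is also the only formal checkpoint: the Protocol (Termination of the trial) has no stopping rules beyond it, and the SAP rules out recalculating the sample size.

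**Working it through.** **1. Is 275 the right base?** Inputs from the Protocol's Sample size calculations: effect 0.35, power 90%, two-sided alpha 0.05, 1.5 parents per family, ICC 0.5, baseline correlation 0.5, 20% loss.
- Unadjusted n per arm for a difference of 0.35 SD: 172
- Design effect: 1 + (1.5 − 1) × 0.5 = 1.25
- Baseline adjustment: 1 − 0.5² = 0.75
- 172 × 1.25 × 0.75 = 161.25; 161.25 / 0.8 = 201.6, so 202 per arm against the stated 206
- 412 / 1.5 = 274.7, so 275 families

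The stated total is reproduced closely, and 275 is a sound base.

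**2. The recruitment bands.**
- Pilot target: 0.50 × 275 = 137.5 families
- 80%: 0.80 × 137.5 = 110
- 60%: 0.60 × 137.5 = 82.5
- Printed count: 99 / 137.5 = 72.0%
- Top of the disputed range: 109 / 137.5 = 79.3%

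So 99 to 109 families is green by count and amber by percentage.

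**3. Can 99 be recovered another way?**
- As 80% of a pilot target: 99 / 0.8 = 123.75, or 247.5 families overall, which is not in the documents
- As 100%: 99, or 198 overall, which is not in the documents
- 80% of 206 parents: 165
- 80% of 110 (half of the 220 families left after 20% loss): 88
- 137.5 × 0.80 × 0.90 = 99 exactly. This multiplies the green recruitment rate by the separate green randomisation rate. The Protocol does not say so, and the result would count families randomised, not recruited.

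**4. What follow-up loss would do to power.** Using N = 412 and the same inputs, effective n per arm = 206 × retention / (1.25 × 0.75). Retention other than 80% is illustrative.

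| Retention | Power |
|---|---|
| 80% | 91% |
| 70% | 87% |
| 60% | 81% |
| 50% | 74% |

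**5. What a 6-month check could show by the decision.** The Timeline starts pilot recruitment on 1 August 2023 and pilot 6-month collection on 1 February 2024, with the funder's decision in April 2024. Families randomised in August and September 2023 fall due by the end of March. Assuming even recruitment:
- 2 × 137.5 / 7 = 39 families (pilot recruitment row, seven months)
- 2 × 275 / 12 = 46 families (12-month recruitment period)
- 95% half-width around 80%: 1.96 × √(0.8 × 0.2 / 39) = 12.6 points; with 46 families, 11.6 points

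**The case against.** **On the count.** The conflict lies only on the green/amber boundary. The red line has no competing number, nothing in the documents makes amber a stop, and the Trial Steering Committee and funder decide on continuation. A reader might infer that the go/no-go decision itself turns on the error; the documents do not support that. A reader might also infer that 99 is simply a slip for 110. The text does not show whether the count, the percentage or the base is wrong, so the supportable request is to reconcile them. These objections stand, but the inconsistency remains.

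**On the recruitment window.** A reader might see a contradiction between the criterion's 6 months and the Timeline's pilot recruitment row (1 August 2023 to 28 February 2024, seven months). It is not one: the criterion is an assessment window that fits inside a longer recruitment period.

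**On the data criterion.** A reader might infer that baseline completeness is bound to be near 100% and so is empty. No denominator is given, recruited and randomised families are distinguished, two parents may respond, and the SAP plans for missing items. The check can be informative, though not about attrition. Nor is retention unwatched: the Protocol monitors it throughout, reports missing-data percentages in the pilot analysis and keeps retention logs. Only a threshold is missing, and whether to set one is partly a design choice. A 6-month check would also be imprecise. The SAP expects recruitment to speed up, so early numbers may be below 39, and reminders may still be running when the report is drafted. All of this limits the second part without removing the mismatch between SAP and Protocol.

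**Conclusion.** The green count is wrong as written against the stated target and bands. It is 11 families below the 80% boundary (110 − 99) and leaves 99 to 109 families with two ratings. This rests only on the 275-family target, which the documents repeat and the arithmetic supports. It is an inconsistency in a decision threshold. It does not touch the treatment estimate, the analysis or the type I error.

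The attrition gap is secondary. The SAP promises information for a criterion that the Protocol does not contain, and the baseline measure cannot supply it. Its consequence should not be overstated: on the plan's inputs, power is still 87% at 70% retention and 81% at 60%. The planned 20% loss is specified for 12 months, so 80% is a borrowed benchmark at 6 months.

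**What to change.** 1. **Reconcile the recruitment line.** On the stated target and percentages: green 110 or more families, amber 83 to 109, red 82 or fewer, out of 137.5. If 99 was intended, restate the percentage or the base it refers to, and say whether families recruited or families randomised are counted.
2. **Align the criteria with the SAP.** Keep the baseline completeness check. Add completeness of the 6-month parent SDQ externalising score among families due by the April 2024 decision, judged against the planned 80% retention. Do not carry over the 75%/50% cut-offs: 75% would rate retention below plan as green, and amber would reach down to 50%, where power is about 74%. Report the number of families and the confidence interval.

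The first change costs one line of Protocol text. The second needs wording in the Protocol and uses data already scheduled from 1 February 2024. Its limitation is that it rests on about 39 to 46 early families at best, so it can reveal gross failure of follow-up but cannot separate, say, 70% from 80% retention.

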The trial manager/research assistants, who have been fully trained in trial procedures, will explain the trial in detail, including randomisation and consent for long-term follow-up using routinely collected data and appropriate data linkage. If happy to take part, informed consent will be obtained from parental/guardian consent and CYP assent obtained from CYP. Verbal consent will be obtained (either via telephone, video conferencing or face-to-face meeting). Research assistants will 'sign' an online consent form on behalf of the participant if they choose to join the trial, evidence of this will be sent to the participant in the form of a PDF document showing the online form on screen. If a participant turns 16 during the course of the trial, they will be re-consented (i.e. asked to complete a consent form for age 16+), before the next data collection/follow-up stage.

A contacts form will be completed for participants including multiple methods of contact (address, telephone, email address) to minimise loss to follow-up. Preferences for follow-up data collection (face-to-face, telephone, online, videoconferencing, or postal) will be obtained to ensure that participants are being contacted in the way that suits them best. They can change their mind at any stage.

Consent will be sought for data (including personal data and special category) to be archived at the end of the trial via the ONS Secure Research Service. This is a condition of taking part in the trial and a requirement of the funder. We have drawn on the YEF template wording for this. Furthermore, data sharing plans will be explicitly included in the participant information sheets.

The right of the participant to refuse to participate in the trial without giving reasons must be respected and participants will remain free to withdraw at any time from the trial without giving reasons and without prejudicing their further treatment. Additionally, parents/guardians will have the right to withdraw their child from the trial at any point if the child is under 16.

Contact details will be securely transferred from the site to the trial team, who will conduct baseline data collection and randomisation. Only when informed consent has been obtained from the participant AND they have been randomised/enrolled into the trial will they be considered a trial participant.

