
[name] – Chief Executive Officer, Triple P UK & Ireland

[name] – Operations Manager, Triple P UK

[name] –Implementation Consultant for Research & Trainer, Triple P UK

Evaluation team

[name] – Co-Principal investigator / Professor, Centre for Educational Development, Appraisal and Research (CEDAR), University of Warwick

[name] – Co-Principal investigator and statistics lead / Assistant Professor in Applied Statistics, Centre for Educational Development, Appraisal and Research (CEDAR), University of Warwick

[name] – Qualitative and process evaluation lead / Assistant Professor, Centre for Educational Development, Appraisal and Research (CEDAR), University of Warwick

[name] – Head of Department/Director, Professor and Cerebra Chair of Family Research, Centre for Educational Development, Appraisal and Research (CEDAR), University of Warwick

[name] – Consultant Clinical and Forensic Psychologist and Approved Clinician, NHS / Professor, Centre for Educational Development, Appraisal and Research (CEDAR), University of Warwick

The project delivery team will be responsible training practitioners and providing intervention support. The local authorities will be responsible for recruiting parents/carers and adolescents. They will then pass the details of the adolescent and their parents/carers to the evaluation team. The evaluation team will check eligibility, consent and complete baseline data collection before parents/carers are randomised by the trial statistician. The evaluation team will complete data collection again at 6- and 12-months post-randomisation.

Risks

A full risk assessment will be completed before trial start. The main areas of risk currently identified are as follows:

Accrual

The delivery team/local authorities may not recruit sufficient numbers of participants. We would work with the delivery team to: (i) ensure that our accrual rate increases over time as the trial gains momentum, and is not set at a rate that is likely to be unachievable, (ii) use a time period for accrual that is realistic, and (iii) consider including additional sites should they be needed.

Adolescent | parent/carers attrition

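### The pilot criteria do not say whether a recruited family is counted before or after randomisation; if before, two green lights can mean only 72% of the six-month milestone randomised.

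*Protocol*

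**What the plan says.** The Internal pilot section of the protocol lists progression criteria. Two matter here.

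- Recruitment: "50% of overall final trial target (families) within first 6 months of recruitment to the trial (green=80 to 100% (n=99" is the printed start of the rule; amber is 60 to 79% and red is below 60%.
- Randomisation: "Proportion of recruited families randomised", with green at 90% or more, amber at 50-89% and red at <49%.

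The family target comes from the protocol's summary table: "275 families, up to 412 parents/carers". Table 2 of the sample size section gives the same 275 families and 412 parents/carers.

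Neither document defines recruited, and the word is used at different stages:

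- Protocol, Recruitment rates: "A total of 412 participants (parent/guardians) will be recruited at an expected rate of 34-35 per month", and "206 participants will be recruited in the pilot phase". These are the powered sample size and half of it.
- Protocol, Informed consent: only with consent "AND they have been randomised/enrolled into the trial will they be considered a trial participant".
- Protocol, Stakeholders and interests: "The local authorities will be responsible for recruiting parents/carers and adolescents". The evaluation team then checks eligibility, takes consent and collects baseline data, and randomisation comes after that.
- Protocol, Timeline: recruitment and randomisation are separate lines.
- SAP, Pilot analysis: randomisation rates are among the things the pilot is meant to inform.
- SAP, Recruitment: the flow diagram has a category for young people who were eligible yet never randomised.

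**The concern.** The two criteria are read together in the decision to continue, so they need a common and stated unit. The larger part of the process text puts recruiting ahead of eligibility checks, consent, baseline and randomisation. On that reading the recruitment light counts families who may never be randomised, yet judges them against half of a total that has to be randomised. The 20% inflation in the sample size is for families lost by the 12-month follow-up, after randomisation. It makes no allowance for loss before randomisation.

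The tolerances of the two lights then multiply, and a pilot that is green on both could have an accrual of randomised families that the same section would call amber. The SAP (Pilot analysis) rules out re-estimating the sample size and describes resources as fixed, so these lights are the main pre-specified check on accrual.

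The number printed in the green band adds to the uncertainty, because it does not match the percentage beside it.

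**Working it through.** **Inputs.** 275 families and 412 parents/carers (protocol summary table and Table 2). Pilot share 50%, recruitment bands 80/60%, randomisation bands 90/50/49%, printed n=99 (Internal pilot). Effect size 0.35, power 90%, two-sided alpha 0.05, mean cluster size 1.5, ICC 0.5, baseline correlation 0.5, 20% loss (Sample size calculations).

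**Step 1: is 275 a number to be randomised?**
- Simple two-group comparison at d=0.35: 172 per arm.
- Design effect: 1 + (1.5 − 1) × 0.5 = 1.25. Baseline adjustment: 1 − 0.5² = 0.75.
- 172 × 1.25 × 0.75 = 161.25 analysed per arm. Dividing by 0.8 gives 202 per arm, 404 in all, within 2% of the planned 412.
- 412 / 1.5 = 274.7, hence 275 families.

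The plan's total is therefore reproduced closely. It is a count at randomisation, inflated only for later loss.

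**Step 2: the milestone and the printed n=99.**
- Milestone: 0.5 × 275 = 137.5 families.
- 80% of the milestone: 0.80 × 137.5 = 110. 100%: 137.5. In parents, 80% of 206 is 164.8.
- None of these is 99. As a share of the milestone, 99 / 137.5 = 72%, which lies in the amber band.
- 0.80 × 0.90 × 137.5 = 99 exactly. The documents do not say whether the figure arose this way.

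**Step 3: fewest randomised families compatible with two greens, by reading.**

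| Reading | Calculation | Randomised families | Share of 137.5 |
|---|---|---|---|
| Recruited is a stage before randomisation, green from 80% | 0.90 × 110 | 99 | 72% |
| As above, but the printed n=99 is the green floor | 0.90 × 99 = 89.1 | 90 | 65% |
| Recruitment counted in randomised families, ratio taken over consented families | 0.80 × 137.5 | 110 | 80% |
| Recruited means randomised in both criteria | ratio always 100% | 110 | 80% |

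In the last row the randomisation criterion carries no information, since it can never be amber or red.

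**Step 4: the bands.** Randomisation is amber at 50-89% and red at <49%, so a value from 49% to below 50% has no colour. Fidelity, adherence and data completeness in the same section use red below 50%, so the ranges meet there.

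**The case against.** Four things can be said in the plan's defence.

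1. *The criteria may already be sound.* Recruitment may be meant in randomised families, with the second ratio taken over consented families. Both lights then work, and two greens guarantee 110 families. This stands as a possible intention, but neither document states it.

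2. *72% is an extreme.* It needs both criteria to sit exactly on their green floors. Green already tolerates 80% on recruitment alone, so compounding adds only the step from 80% to 72%. This stands, and is a main reason for rating the point minor.

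3. *The lights do not decide by themselves.* The Trial Steering Committee and the funder decide at month 12. The regular committee reports include screening and recruitment summaries and plots of actual against predicted recruitment. The SAP expects recruitment to gather pace, and the protocol's Risks section allows for additional sites. This also stands.

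4. *The n=99 may show that the compounding was noticed,* since it equals the product of the two floors. That cannot be confirmed or excluded from the documents. If so, it is printed beside the wrong percentage.

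Two stronger readings are tempting. A reader might infer from Recruitment rates and Informed consent that recruited means randomised, so that the randomisation criterion is empty by construction. But the consent section defines a trial participant, not a recruited family. The protocol also uses participant freely for people still being screened (Procedure), and most of the process text puts recruitment first.

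A reader might also infer that two greens leave the trial short of its power. As an illustration, if a 72% pace held through both halves, 0.72 × 275 = 198 families would be randomised. Then 198 × 1.5 × 0.8 / 2 = 118.8 analysed per arm, and power under the plan's assumptions would be about 80%, against about 91% by the same formula at 275. Nothing in the documents says that the pace would persist, and recruitment continues after the pilot towards an unchanged target.

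**Conclusion.** The point holds as a minor one. The term recruited is undefined in two linked progression criteria. On the better-supported reading, in which recruitment precedes randomisation, green on both is compatible with as few as 99 randomised families. That is 72% of the six-month milestone of 137.5, and amber on the protocol's own recruitment scale. If the printed n=99 is itself the floor for recruited families, the minimum falls to 90, about 65%. If recruitment is counted in randomised families, it is 110, or 80%.

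These are minimum passing counts against a pilot milestone. They rest on the 275-family target and on the published bands, and they do not forecast accrual or show that 275 families or 90% power will be missed. The disagreement between n=99 and 80% of 137.5, and the unclassified values from 49% to below 50%, are plain on the page and do not depend on how recruited is read. The validity of the final analysis is not affected; only the clarity of the progression decision is.

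**What to change.** In the Internal pilot section of the protocol:

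- State the recruitment criterion in randomised families against 137.5, and correct or explain n=99 (80% is 110).
- Define the randomisation criterion as families randomised divided by families consented and confirmed eligible.
- Set the red band for randomisation at below 50%, in line with the criteria that follow it.

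The denominator should come from consent records together with the flow-diagram counts in the SAP's Recruitment section. That diagram is specified in young people, so the counts need to be kept by family as well. The contact log alone is not enough, because it is described as holding those who were ineligible, or eligible but not consented or approached.

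The cost is a few lines of text and a family-level tally of steps already being recorded. The one downside is that the recruitment light becomes slightly harder to turn green.
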